11.5 Please provide a justification for your sample size

11.6 Data Analysis Plan:

Statistical Analysis: Baseline comparability between treatment groups will be evaluated with respect to entry criteria, as well as demographic characteristics and baseline symptoms and assessment measure scores. We will use summary statistics and graphical techniques, such as box plots, to compare the baseline characteristics of treatment groups. Prior to conducting the main analyses, we will do checks via *t*-test and Chi-square to evaluate whether the randomization procedures resulted in groups with meaningful differences with regard to demographic factors such as age and ethnicity, AUD and/or PTSD symptom severity, subjective impressions of alcohol's reinforcing effects, and alcohol craving (PACS). Should we identify significant differences on any of these parameters, they will be taken into account statistically through covariation procedures. Since randomization will be blocked on assignment to the stratifying variables, we do not anticipate differences across conditions in those variables. We will also evaluate whether there are systematic differences (again via *t*-test and Chi-square) with regard to the individual characteristics noted above among those randomized that do and do not complete the study. In addition, we will generate summary descriptive statistics for each of these different subgroups and the overall sample.

Secondary analyses: In addition to the major analyses designed to address the study aims, the following secondary analyses will also be conducted:

Treatment retention: Between group comparisons via Chi-square will be conducted to determine whether the prazosin condition was more likely to complete the medication phase of the study. Study completion will be operationalized such that study completers will have attended at least 10 of the 14 interim study visits and the visit at 13-weeks when study participation is completed. We will also use *t*-test to compare the number of study visits attended overall by the two groups.

Study drug compliance: We will report descriptive statistics for pill counts to determine adherence. We will use *t*-tests to compare medication compliance across the two study conditions. Since prior work shows that individuals on active medication with 80% or greater medication adherence have superior outcomes to non-adherent individuals,⁹³ participants who achieve $\geq 80\%$ adherence will be defined as adherent.

Adverse events: Descriptive statistics regarding the number, severity, and types of adverse events reported by participants in the two conditions will be generated. Depending on the types of between group differences (e.g., type vs. severity vs. number) detected, if any, significance testing via *t*-test or Chi-square will follow.

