The proposed study is a 21-week, titration to stable dose, randomized, two-group parallel-design, double-blind, placebo-controlled trial to evaluate the efficacy of prazosin for decreasing alcohol use in 200 active duty Service Members (SMs) who are receiving standard outpatient treatment for AUD at JBLM. Treatment groups will be stratified by presence or absence of PTSD and by assignment to Behavioral Health treatment group, the Moderate Intensity treatment group or the High Intensity treatment group. We are requesting to consent up to 300 Service Members to randomize 200 to study drug to have 120 study completers.

Prazosin is an FDA approved drug that is being used off-label for investigational purposes in this study.

Exemptions for an Investigational New Drug (IND) application to the FDA:

This study will be conducted using the drug, prazosin, which has been approved by the FDA for the following indication(s): treatment of hypertension.

Pursuant to AR 40-7, paragraph 4-12, "Use of an Approved Drug for an Unapproved Indication," this study does not require the acquisition of an IND number from the FDA. All conditions listed in this paragraph as "a-e" are met by this clinical investigation. Additionally, Department of Health and Human Services "Investigational Use of Marketed Products" guidelines, dated February 1989, indicate an IND number is not required in the conduct of this study.

(a) The investigation is not intended to be reported to the FDA as a well-controlled study in support of a new indication for use, nor intended to be used for any other significant change in the labeling for the drugs.

(b) The drugs undergoing investigation are lawfully marketed as prescription drug products, and the investigation is not intended to support any other significant change in the advertising for the drug products.

(c) The investigation does not involve a route of administration or dosage level or use in a patient population or other factor that significantly increases the risks (or decreases the acceptability of the risks) associated with use of the drug products.

(d) The investigation is conducted in compliance with the requirements for human use review and informed consent set forth in AR 40-38.

(e) The drug is not represented in a promotional context as being safe or effective for the purposes for which it is being investigated.

9.6 Target Population:

Describe the population to whom the study findings will be generalized

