11.0 Statistical/Data Analysis Plan

11.1 Statistical Considerations:

List the statistical methods to be used to address the primary and secondary objectives, specific aims, and/or research hypotheses. Explain how missing data and outliers will be handled in the analysis. The analysis plan should be consistent with the study objectives. Include any sub-group analyses (e.g., gender or age group). Specify statistical methods and variables for each analysis. Describe how confounding variables will be controlled in the data analysis

Primary Outcome Measures: Analysis of the primary outcomes will follow the ITT principal. For each of the two outcomes, a linear regression model with covariates that include treatment group, the stratifying variables, and baseline value of the outcome will be used to compare the prazosin and placebo groups at 13 weeks. In addition, we will conduct a repeated measures analysis using data from the two points of follow-up (8 and 13 weeks). The repeated measure analysis will be conducted by comparing response profiles between prazosin and placebo groups. An initial comparison will be conducted using the general estimating equations (GEE) method of Liang and Zeger,⁹¹ which allows all observed data points for each participant. Secondarily, an analysis of covariance (ANCOVA) rate of change analysis will be done as a confirmatory or sensitivity analysis. Stratifying variables will be included as covariates in each model since they are factors in the stratification. It is anticipated that a retrieved dropout strategy will

result in a limited number of missing observations. For the GEE analysis no imputation strategy is required. For the ANCOVA analysis the missing data patterns will be evaluated between the treatment groups. If the patterns are similar and the magnitude of missing data is small, a conventional last observation carried forward (LOCF) imputation will be performed. If the amount of missing data is substantial and/or the patterns of missingness disparate, as an alternative to the traditional ANCOVA, the summary statistic method of Dawson⁹² will be employed. This method has been shown to be robust to non-ignorable missingness. The approach summarizes the response profile using a least square slope, and stratifies on the missing data pattern. We will also run analyses to assess the interactions between treatment group and gender.

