A completers analyses will be done in a similar fashion for the primary outcome measures, using only the cases that remained on protocol throughout the 13-week study drug period.

Secondary outcome measures: All secondary outcome measures (PSQI, CAPS, PCL-M, SIP, and biological markers) will be analyzed in a manner similar to that described above for the primary outcome measures. (We will also perform exploratory analyses in a similar manner on the CAPS symptom clusters and individual CAPS items to generate hypotheses about differential responsiveness to prazosin for AUD relative to response of individual PTSD symptom clusters/symptoms).

Procedures to minimize missing data: Although all efforts will be made to complete study visits in person, it may be necessary to obtain assessments by telephone. Attempts will be made to reach the participant by telephone. The following actions will be attempted (as appropriate per visit schedule): 1) adverse events will be assessed by telephone, 2) assessments shall be completed by telephone interview with the raters, 3) self-rated measures will be done by mail using prepaid envelopes, and 4) dispensing of study drug shall be done by traceable shipment. No-show, missed visits and actions taken will be documented in the study record.

11.2 Sample Size:

Sample Size Estimation: The power analysis is based on two types of preliminary data: the results of [name] study of prazosin for reduction of alcohol use in persons with AUD without PTSD and the preliminary results of our study of prazosin for combat trauma PTSD in active duty SMs without AUD in which we obtained the PACS. There were 19 completers in [name] pilot study. Standard drink units in the final month of the study drug period were 30.3 ± 32 (mean \pm SD) ($N=10$) in the prazosin group and 62 ± 58 ($N=9$) in the placebo group ($F=1.50$, $p=0.012$). There were 53 completers in the prazosin study for combat trauma PTSD in active duty SMs. The difference (delta) in PACS scores were -2.6 ± 5.8 ($N=27$) vs. -0.3 ± 3.3 ($N=26$) in the prazosin vs. placebo groups, respectively, $t=-1.74$, $p=0.04$ (one-tailed).

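### Beyond the baseline outcome and strata, extra covariates are chosen by baseline significance tests, so the final efficacy models are not fixed in advance

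*Combined protocol and SAP*

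**What the plan says.** Section 11.1 (Statistical Considerations) sets the core of the primary model in advance: "a linear regression model with covariates that include treatment group, the stratifying variables, and baseline value of the outcome will be used" to compare the arms at 13 weeks. It adds: "Stratifying variables will be included as covariates in each model since they are factors in the stratification". Under Section 9.5 the strata are PTSD status and the treatment group (Behavioral Health, Moderate Intensity or High Intensity). Secondary outcomes "will be analyzed in a manner similar to that described above for the primary outcome measures".

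Section 11.6 (Data Analysis Plan) adds a second rule: "Prior to conducting the main analyses, we will do checks via *t*-test and Chi-square" for differences between the arms. Six items are named: age, ethnicity, AUD severity, PTSD severity, perceived reinforcing effects of alcohol, and PACS craving. The list is open, because the demographic items are given only as examples. The consequence follows: "Should we identify significant differences on any of these parameters, they will be taken into account statistically through covariation procedures". The section gives no significance level and does not say which models the rule governs (week-13 regression, GEE, ANCOVA, completers or secondary outcomes).

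**The concern.** Under 1:1 randomisation the null hypothesis of a baseline test between arms is true by design, so a significant result is a chance finding. What makes a covariate useful is how well it predicts the outcome, and the test does not measure that. The rule adds a variable because it happens to be imbalanced and leaves out a strong predictor that happens to be balanced. If the tests are meant to detect a failure of randomisation, covariate adjustment is not the remedy.

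Two things are at stake. First, the covariate set beyond the core is unknown until the arms have been compared, and the rule cannot be programmed as written. AUD severity could be the AUDIT, the SIP or a calendar measure. PTSD severity could be the CAPS or the PCL-M. No instrument described in Section 10.2 is said to measure perceived reinforcing effects. PACS is a fixed covariate in the PACS model and also on the test-triggered list. Second, baseline data already collected could sharpen the treatment estimate, and this rule makes little use of them. That matters more for PACS, a primary measure, which the plan powers at only 76% two-sided.

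**Working it through.** **1. The plan's own power figures (Section 11.2), 60 per arm, two-sided 0.05.** Power = Φ(d·√(n/2) − 1.96), with d = difference / √((SD₁² + SD₂²)/2).

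- PACS change: −2.6 (SD 5.8) against −0.3 (SD 3.3). Pooled SD = √((5.8² + 3.3²)/2) = 4.72, and d = 2.3/4.72 = 0.487. Power = Φ(0.487 × 5.477 − 1.96) = Φ(0.71) = 76.1%; the plan states 76%.
- Standard drink units: 30.3 (SD 32) against 62 (SD 58). Pooled SD 46.84, d = 31.7/46.84 = 0.677. Power 96.0% (96.5% with the SD weighted by degrees of freedom); the plan states 97%.

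Both are two-group comparisons of means that do not use the covariate rule, so they do not depend on this point.

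**2. How often the rule changes the model.** Assume a 0.05 level (none is stated) and independent tests. The chance that at least one variable enters is 1 − 0.95^k.

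- k = 5 (the named items less PACS, which is already in the PACS model): 1 − 0.95⁵ = 22.6%.
- k = 6 (all named items, as in the drinking model): 1 − 0.95⁶ = 26.5%.
- k = 10 (if the open list grows): 40.1%.

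Positive correlation between the tested variables would lower these figures.

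**3. What the rule and a fixed list each deliver.** Simulation: 12,000 trials per setting, 60 per arm, baseline outcome in every model, five further independent covariates, effect 0.487 SD. Extra R² is the share of outcome variance that the five explain beyond the baseline outcome. The documents give no value, so a range is used. The Monte Carlo standard error of a power near 75% is √(0.75 × 0.25/12,000) = 0.4 points.

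| Extra R² | Power: core model only | Power: test-triggered | Power: all five prespecified | Prespecified minus triggered | Type I error, triggered |
|---|---|---|---|---|---|
| 0.05 | 74.7% | 74.4% | 75.0% | 0.6 | 4.8% |
| 0.10 | 75.3% | 75.3% | 77.9% | 2.6 | 5.0% |
| 0.20 | 75.2% | 75.4% | 82.0% | 6.6 | 4.4% |

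The triggered rule stays within 0.3 points of having no extra covariates. At extra R² 0.20, the simulated SD of the estimated effect is 0.183 with the core model, 0.179 with the rule and 0.168 with the fixed list.

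**4. Check by formula.** Dividing the PACS SD by its adjusted value, power = Φ(0.487 × 5.477/√(1 − R²) − 1.96) gives 78.2%, 80.4% and 84.7% at R² 0.05, 0.10 and 0.20. These are gains of 2.1, 4.2 and 8.6 points over 76.1%. The formula ignores the cost of estimating five coefficients, about 5/112 = 4.5% in variance with 120 − 8 = 112 residual degrees of freedom. That nearly cancels the benefit at R² 0.05, so the formula gives upper values.

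**The case against.** The strongest defence is that the core model is already sound. A reader of Section 11.6 alone might infer that covariates enter only after a significant baseline test and that the precision from baseline data is lost. Section 11.1 rules this out: the baseline outcome and the strata, including PTSD status, are in the model whatever the tests show. Only additional covariates are in question.

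A reader might also infer a validity problem. None is shown. The tests use baseline data and precede the main analyses, so the trigger does not depend on treatment results, and simulated Type I error is 4.4–5.0%.

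Nor do the documents support a large power gain as a firm figure. Assuming that baseline variables explain 20–30% of the variance, and starting from an unadjusted model, one could obtain 6–11 points. The plan's model is never unadjusted, and candidates such as CAPS total overlap the PTSD stratum. The PACS effect size also comes from change scores, so its SD already reflects some use of the baseline.

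All of this stands and limits the size of the point. It does not rescue the rule, which is a stated method with no prognostic basis, no level and an open list. With about 40% dropout expected, imbalance among those analysed need not be pure chance, but that argues for naming prognostic covariates beforehand.

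**Conclusion.** The point holds, at modest size. Section 11.6 lets chance imbalance decide whether covariates are added to a core that Section 11.1 fixes. At an assumed 0.05 level with independent tests, the model changes in about 23–27% of trials for five or six variables. The rule gains essentially no power. A prespecified list would gain about 1, 3 and 7 points of PACS power over it at extra R² 0.05, 0.10 and 0.20, and at most about 2, 4 and 9 by the formula. Which of these applies is unknown, because the documents give no R². The conclusion does not need a power gain: even at zero gain, an undefined test-driven rule leaves the final models open. No bias, Type I inflation or error in the stated power is claimed.

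**What to change.** Delete the test-then-adjust sentence in Section 11.6 and make the comparison of arms at baseline descriptive, using the summary statistics and box plots already planned. The comparison of completers with non-completers can stay, since it is not between randomised arms.

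State that the Section 11.1 covariates (treatment, strata, baseline value of the outcome) apply to all efficacy analyses. If more precision is wanted, add a short list, named before any comparison by arm, of prognostic baseline variables already collected. Examples are PACS in the drinking model, calendar drinking in the PACS model, AUDIT score and CAPS total, each with its instrument and scoring stated. The list should be short, because weak predictors return almost nothing.

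The cost is SAP wording and a few degrees of freedom out of 120 expected completers. If no extra covariates are wanted, deleting the sentence alone fixes the model.

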12.0 Participant Information

12.1 Subject Population:

Participants will be 300 consented, 200 randomized SMs with concurrent AUD with or without PTSD. Specific Inclusion and Exclusion criteria for these participants are described in detail below. All participants will be in stable medical health. Racial, ethnic, and gender distribution of the participants is expected to mirror that of SMs being treated in the DBH clinics from which they will be recruited; i.e., 70% Caucasian, 21% African American, 6% Asian American/Pacific Islander, 3% Native American; Hispanic ethnicity 10%; 10% women, 90% men. Because the proposed study specifically addresses treatment of AUD in active duty SMs, all participants will be over the age of 21.

12.2 Age Range:

Check all the boxes that apply. If the age range of potential subjects (specimens, records) does not match the range(s) selected, please specify in the text box.

- 0-17
- 18-24
- 25-34
- 35-44
- 45-54
- 55-64

65-74
 75+

12.3 Gender:

Male
 Female
 Other

12.4 Special categories, check all that apply

Minors /Children
 Students
 Employees - Civilian
 Employees - Contractor
 Resident/trainee
 Cadets /Midshipmen
 Active Duty Military Personnel
 Wounded Warriors
 Economically Disadvantaged Persons
 Educationally Disadvantaged Persons
 Physically Challenged (Physical challenges include visual and/or auditory impairment)
 Persons with Impaired Decisional Capacity
 Prisoners
 Pregnant Women, Fetuses, and Neonates
 Non-English Speakers
 International Research involving Foreign Nationals - Headquarters Review is necessary

You must also consider the requirements of DoDI 3216.02, Enclosure 3, paragraph 7.e.

Depending on your intended subjects' status, you may also need to consider the requirements of DoDI 3216.02, Enclosure 3, paragraph 7.e.

You must also consider the requirements of 32 CFR 219.111(b).

12.5 Inclusion Criteria:

Order Number	Criteria
1	Male or female active duty personnel over the age of 21 with a current DSM-IV diagnosis of Alcohol Abuse or Dependence or a current DSM-V diagnosis of Alcohol Use Disorder
2	Recent alcohol consumption: more than 14 (women) or 21 (men) drinks per week for at least 2 weeks in the past 60 day period OR at least 2 days of heavy drinking in the past 60 day period (4 or more drinks for women and 5 or more drinks for men)
3	Good general medical health (see Exclusion Criteria)

4	Women of childbearing potential must agree to abstain from sexual relations that could result in pregnancy or use an effective method of birth control acceptable to both participant and the study clinician during the study. Men are not required to use contraception during the study.
5	Concomitant use of naltrexone and/or Antabuse must be stable for 2 weeks prior to Baseline.
6	Capacity to provide informed consent
7	English fluency

12.6 Exclusion Criteria:

Order Number	Criteria
1	Current diagnosis of opioid, methamphetamine, cocaine, marijuana, or other illegal substance dependence or abuse.
2	Signs or symptoms of alcohol withdrawal at the time of initial consent
3	Current diagnosis of schizophrenia, other psychotic disorder, manic phase of bipolar disorder, or cognitive disorder.
4	Suicide attempt or suicidal ideation with intent in the past month.
5	Significant acute or chronic medical illness, including unstable angina, recent myocardial infarction, history of congestive heart failure, preexisting hypotension (systolic <100) or orthostatic hypotension (defined as a systolic drop > 20mmHg after two minutes standing accompanied by lightheadedness or syncope); insulin-dependent diabetes mellitus; chronic renal or hepatic failure, acute pancreatitis, Meniere's disease. Liver function tests more than 5 times the upper limit.
6	Concomitant use of trazodone (due to increased risk of priapism). There will be a two week trazodone washout period before the baseline visit
7	Concomitant use of an alpha-1 blocker medication or insulin
8	Use of prazosin in the 4 weeks prior to Baseline
9	History of prazosin sensitivity/allergy
10	Not suitable for study per the clinician's judgement
11	Participants who use erectile dysfunction (ED) medications (avanafil, sildenafil, tadalafil, or vardenafil) will be asked to abstain from ED drug use during the study titration phase and then may use ED drugs at one-half the customary dose during study participation
12	Use of bodybuilding/weightlifting supplements with vasodilator properties

13.0 Recruitment and Consent

13.1 Please describe the recruitment process, including how subjects will be identified and selected for the study.

Participants will be recruited from SMs DBH treatment programs including Substance Use Disorders Clinical Care (SUDCC). No participant will be excluded based upon race, ethnicity, or gender. Racial, ethnic, and gender distribution of the participants is expected to mirror the demographics of SMs undergoing treatment in the DBH. SMs enter these programs from multiple referral sources: self-referral, command direction, medical referral, etc.

The number of SMs referred to the standard outpatient alcohol treatment programs is approximately 150 per month for pure AUD without concomitant use of other drugs of abuse (e.g., marijuana, cocaine, methamphetamine, DMA, and opiates). The average age is 24 with a range of 21-55 years. The racial composition is 70% Caucasian, 21% African American, 6% Asian American/Pacific Islander, 3% Native American. The Hispanic ethnicity of the referred population is 10% Hispanic, 90% non-Hispanic. Gender composition is 10% women, 90% men.

We will not enroll any members of “special vulnerable populations.” Although SMs may have command requirements to complete the clinical outpatient JBLM assignment to the SUDCC programs, command pressure to participate in this research study will be strictly avoided. If a participant becomes incarcerated for longer than one day after the Baseline, the participant will be discontinued from the study. Participants who have been discontinued from the study during the screening phase (e.g., do not currently meet inclusion/exclusion criteria) may be re-screened at a later date. Those discontinued following randomization will not be eligible for re-enrollment.

13.2 Compensation for Participation:

Under 24 USC 30, payment to Federal Employees and Active Duty military personnel for participation in research while on duty is limited to blood donation and may not exceed \$50 per blood draw. They may not receive any other payment or non-monetary compensation for participation in a research study unless they are off duty or on leave during the time they are participating in the protocol.

Participants will be compensated with a \$50 gift card per blood draw (up to five blood draws total, up to \$250 value). They will receive a \$50 gift card after each visit at which a blood draw is performed (screen, baseline, weeks 8, 13 and 19).

13.3 Please describe the pre-screening process. If no pre-screening, enter Not Applicable in the text editor

Formal psychiatric and medical screening: After written informed consent is obtained, a formal screening visit will be performed. At this visit, basic demographic information will be obtained (gender, age, racial and ethnic identification, and educational attainment). Military/deployment history will be collected and reviewed. Medical records will be reviewed for medical/psychiatric diagnoses, recent treatment, lab results, and medications.

Participants will be interviewed using the Structured Clinical Interview for DSM-IV (SCID-IV) to document DSM-IV diagnosis of Alcohol Abuse or Dependence and to rule out exclusionary psychiatric disorders. The Clinician-Administered PTSD scale (CAPS) will be completed to confirm PTSD diagnosis (used as a stratifying variable) and for baseline measure of PTSD severity.

Medical screening will include review of medical history and medications, and screening physical exam. Blood pressure (BP) and heart rate (HR) will be measured after the participant has been seated or lying down for at least 10 minutes and again after the participant has been standing for 2 minutes (seated/supine and standing BP and HR). Approximately 7 ml of blood will be drawn for liver function tests (AST, ALT). Clinical labs (chemistry panel and complete blood count) will be drawn if clinically indicated. If the additional labs are drawn, a total of 15 ml of blood will be drawn at the screen visit. A routine urinalysis will be done if clinically indicated. Twelve-lead EKG will be obtained if clinically indicated (i.e., history of cardiac disease, arrhythmia, or symptoms of potential cardiac origin such as chest pain).

Female participants of childbearing potential will have a urine pregnancy test. Pregnant or nursing women are not eligible for study participation. Women of childbearing potential must agree to abstain from sexual relations that could result in pregnancy or use an effective method of birth control acceptable to both participant and the study clinician during the study. Men are not required to use birth control during the study.

13.4 Consent Process:

Are you requesting a waiver or alteration of informed consent?

Yes No

Please explain the consent process:

The study will be explained to eligible participants by one of the approved study personnel in a private setting. DBH personnel will not conduct the initial consent visit.

Potential participants will be given ample opportunity to read the consent form and will be encouraged to ask questions. If the potential participant wishes to have a relative or friend present during the consent process, we will accommodate the potential participant. If a potential participant wants to take the consent home for further consideration before agreeing to participate, he or she will have that opportunity.

Written informed consent/HIPAA authorization will be obtained from participants. The signed consent form and a note documenting consent will be placed in the participant's research record.

The following elements will be discussed with the potential participant:

- The purpose and objectives of the study
- The length of the study
- Any potential risks, discomfort and inconvenience
- The importance of following study procedures
- The importance of compliance with all assessments and study visits
- The possibility of the need for unscheduled visits
- Randomization – there is a 50/50 chance of being randomized to either treatment (active medication or placebo)
- Participation is entirely voluntary and the participant may withdraw from the study at any time without loss of benefits to which he/she may otherwise be entitled
- Alternative treatments
- Provisions for keeping study data confidential and exceptions to confidentiality
- Adverse events are treated at no cost to the participant

Care will be taken to assure that each participant's current treatment and future services and benefits are not contingent on participation in this or any research study. The voluntary nature of research study participation will be emphasized. The participant must sign the informed consent/HIPAA authorization form before any study procedures are performed.

13.5 DoDI 3216.02 requires an ombudsman to be present during recruitment briefings when research involves greater than minimal risk and recruitment of Service members occurs in a group setting. If applicable, you may nominate an individual to serve as the ombudsman.

N/A
 Propose ombudsman

13.6 Withdrawal from Study Participation:

Explain the process for withdrawal and specify whether or not the subjects will be given the opportunity to withdraw their data their data/specimens in the event they wish to withdraw from the study

Study Discontinuation or Termination: If the participant is not able to tolerate a minimum dose of 3 mg /day of placebo/prazosin, he or she will undergo early termination and all week 13 assessments will be performed; the participant will be referred to his/her primary mental health care provider for further management. Reasons for early discontinuation or withdrawal will be recorded.

Participants may be discontinued prematurely from study treatment to manage deterioration of clinical status. Specifically, dangerousness toward self or others or emergence of acute psychiatric symptoms necessitating hospitalization will result in discontinuation from the study. If at any time during the study, psychiatric symptoms become markedly increased resulting in severe participant distress or presenting immediate danger to self or others, the participant will be discontinued from the study. In case of need for increased level of care or emergent care, study personnel will provide a warm hand-off to DBH personnel. DBH personnel will assume responsibility for arranging appropriate care.

